3.6 Archive of data

The investigator must retain all study documentation pertaining to the conduct of the study at the study site for a period of at least 5 years.

3.7 Ethical and administrative endorsement

The study was approved by the Institutional Review Board (IRB) of the University of Hong Kong and Hospital Authority (IRB reference number: to be added when approved)

4. SELECTION AND ENROLLMENT OF PARTICIPANTS

4.1 Selection of study population at in-patient

4.1.1. Inclusion criteria

1. Admitted to the acute medical ward of Queen Mary Hospital via the accident and emergency department
2. Aged 18 years or above
3. Hospitalized for less than 24 hours at the time of recruitment
4. Presented with exacerbation of underlying lung disease, acute coronary syndrome or stroke
5. Competent and agree to provide written informed consent

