2. BACKGROUND AND RATIONALE

2.1. Background and study rationale

Respiratory viruses cause severe infections, and contribute to a substantial number of hospitalizations, admission to intensive care units and deaths (1). Many hospitalizations due to respiratory virus infection are related to pneumonia or exacerbation of chronic lung disease. In addition, many hospitalizations are related to extrapulmonary complications, such as acute coronary syndrome or stroke (2).

Previous studies have reported the incidence of respiratory viruses among patients with pulmonary complications (3), or the association of respiratory viruses with acute coronary syndrome or stroke (4). However, there are several problems associated with these studies. First, many of these studies are retrospective in nature, and therefore testing was only performed in selected patients with respiratory symptoms. Hence, many patients without respiratory symptoms were not recruited. Second, respiratory virus can be detected in some asymptomatic individuals. Therefore, the presence of respiratory virus may be an incidental finding rather than the cause of the complication. Third, many studies only focus on a few respiratory viruses, especially on influenza virus.

This study aims to address these issues. We propose to conduct a prospective cohort study. We will recruit hospitalized adult patients with exacerbation of underlying lung disease, acute coronary syndrome or stroke. As controls, we will recruit outpatients follow-up for chronic heart disease, chronic lung disease or neurological conditions. We will collect saliva from study participants and perform respiratory virus testing using a multiplex PCR panel. Our previous studies have shown that there is a high concordance between results from respiratory virus testing on saliva and nasopharyngeal specimens (5, 6).

Our study will provide accurate data on the epidemiology of respiratory viruses in pulmonary and extrapulmonary complications. These data are important for clinicians, public health practitioners and scientists.

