3.2 Study design and organization

3.2.1 Overall study design

This is a prospective cohort study involving hospitalized adult patients admitted to the acute medical ward of Queen Mary Hospital, an acute care university-affiliated hospital with 1,700 beds in Hong Kong. Patients will be screened for eligibility based on inclusion and exclusion criteria. Written informed consent will be obtained from all study participants. Saliva specimens will be collected from study participants, and will be tested for respiratory viruses using a multiplex PCR panel. Patients' demographics, underlying diseases, and outcome measures will be collected.

Since respiratory viruses can be detected in asymptomatic adults, we will also recruit outpatients followed up for a chronic condition to determine the frequency of respiratory viruses among these patients without any acute symptoms requiring hospitalization. We will adjust the crude incidence from this background rate.

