4.2 Selection of study population at out-patient

4.2.1 Inclusion criteria

1. Aged 18 years or above
2. Follow-up at out-patient clinic or at the physiotherapy department of Queen Mary Hospital
3. Competent and agree to provide written informed consent

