6.2 Analysis of the study

Crude incidence of each respiratory virus and overall respiratory virus infection among hospitalized patients and out-patients will be estimated. To adjust for the background rate of respiratory virus detection among out-patients, we will calculate adjusted population attributable fraction (aPAF) as described previously (22). Conceptually, aPAF represents the fraction of hospitalization that can be attributed to a particular pathogen. Death rate of each detected respiratory virus and overall respiratory virus infection among patients in the acute medical wards will be estimated.

For symptomatology of respiratory viruses, frequencies and proportions of respiratory and non-respiratory symptoms for each respiratory virus and overall respiratory virus infection will be calculated.

Statistical test will be performed using SPSS version 23.0. A *P* value of <0.05 with two-sided testing will be considered statistically significant.

7. STUDY TEAM and STUDY SITE

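### Every control must already be under follow-up at the hospital but in-patients need not be, so the out-patient background rate behind the aPAF may not describe the population that in-patients without such follow-up come from

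*Combined protocol and SAP*

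**What the plan says.** **In-patients (section 4.1.1).** The entry route is "Admitted to the acute medical ward of Queen Mary Hospital via the accident and emergency department" and the presenting condition is "Presented with exacerbation of underlying lung disease, acute coronary syndrome or stroke". Only the lung group must have a pre-existing disease. No criterion in 4.1.1 or 4.1.2 asks whether the patient attended this hospital before.

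**Controls (section 4.2.1).** Each must meet "Follow-up at out-patient clinic or at the physiotherapy department of Queen Mary Hospital". This criterion names no disease. Section 2.1 describes the group more narrowly: "As controls, we will recruit outpatients follow-up for chronic heart disease, chronic lung disease or neurological conditions". Section 3.2.1 says "we will also recruit outpatients followed up for a chronic condition to determine the frequency of respiratory viruses among these patients".

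**Use of the control rate.** Section 3.2.1 states "We will adjust the crude incidence from this background rate". Section 6.2 calculates an aPAF, citing reference 22 for the method, and interprets it thus: "Conceptually, aPAF represents the fraction of hospitalization that can be attributed to a particular pathogen". The aPAF is the second objective in section 3.1 and part of the primary objective in the synopsis. The plan states no matching, names no adjustment covariates, does not split in-patients by prior follow-up and has no other control group.

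**The concern.** Controls in an attributable-fraction analysis stand in for the people who gave rise to the cases. Their detection rate is meant to show how often a virus would be found in those people without the acute event. Section 2.1 relies on this: it criticises earlier work because a detected virus may be incidental, and the out-patient rate is the plan's answer.

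Here one group is selected on follow-up at the hospital and the other is not. An in-patient without such follow-up could not have been chosen as a control before the admission. If people under follow-up differ from others in vaccination, contacts or virus carriage, the aPAF combines any effect of the virus with a difference between source populations. The reported fraction of hospitalization attributed to a virus could then be too high or too low, and no planned analysis would show it.

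**Working it through.** **Step 1. Eligibility side by side.**

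| | In-patients (4.1) | Controls (4.2) |
|---|---|---|
| Entry | Emergency admission to the acute medical ward | Out-patient clinic or physiotherapy follow-up |
| Prior follow-up at this hospital | Not required | Required of all |
| Prior disease | Required for the lung group only | None named in 4.2.1; chronic disease in 2.1 and 3.2.1 |
| New symptoms in the past 14 days | Not an exclusion | Excluded |

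In-patients without prior follow-up are therefore eligible in all three diagnosis groups. An underlying lung disease can be managed elsewhere. A first coronary event or stroke can occur in someone who attends no clinic, or in someone who already attends one here for another reason.

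**Step 2. Inputs for an illustration.** The documents give no detection rates, no share of in-patients under follow-up, and the aPAF formula only by citation. All of the following are assumptions:

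- detection in in-patients p1 = 0.20, the same with and without prior follow-up
- detection in controls p0 = 0.08
- share of in-patients without prior follow-up = 0.40
- background in the population those patients come from = 0.05, 0.11 or 0.14
- aPAF = (p1 - p0)/(1 - p0), which is algebraically the same as p1(OR - 1)/OR when OR is the crude odds ratio

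**Step 3. Figure the plan would report.** (0.20 - 0.08)/(1 - 0.08) = 0.12/0.92 = 13.0%.

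**Step 4. aPAF among in-patients without follow-up.**

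- background 5%: 0.15/0.95 = 15.8%
- background 11%: 0.09/0.89 = 10.1%
- background 14%: 0.06/0.86 = 7.0%

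**Step 5. Overall aPAF, as the weighted sum of the two parts.**

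- background 5%: 0.6 × 0.1304 + 0.4 × 0.1579 = 14.1%
- background 11%: 0.6 × 0.1304 + 0.4 × 0.1011 = 11.9%
- background 14%: 0.6 × 0.1304 + 0.4 × 0.0698 = 10.6%

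Pooling the backgrounds first (6.8%, 9.2%, 10.4%) and applying the formula once gives 14.2%, 11.9% and 10.7%, so the choice hardly matters. The shift from 13.0% is about +1.1, -1.2 or -2.4 percentage points. If the two backgrounds are equal, it is zero.

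**Step 6. Sampling error for scale.** With 100 controls (section 6.1) and 8 positive, the exact 95% interval for the background is 3.5% to 15.2%. All three alternative backgrounds lie inside it.

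**The case against.** The strongest reply has four parts.

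- **Clinic controls are a pragmatic choice** for measuring detection without acute illness in a study whose size is set by budget (section 6.1). The primary outcome in 3.3.1, incidence of respiratory viruses, does not depend on them. Both statements are correct and limit the weight of the point. They do not protect the aPAF.
- **The word adjusted, and the cited method, may bring in covariates.** Section 5.2 collects age, sex, comorbidities, vaccination and symptomatic close contacts, which covers some routes by which the groups could differ. This stands in part. But section 6.2 names no covariates, and adjustment cannot supply controls who are not under follow-up.
- **No document shows that detection differs by follow-up status.** This stands in full: the mismatch is in the text, but bias is only possible.
- **The shift is small beside the sampling error** of a 100-patient control group. This stands for the illustration. However, sampling error is shown by an interval, whereas a source-population difference would not be visible in one.

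A reader might go further and infer that first-ever coronary and stroke cases are the ones outside the control population, so that the problem lies mainly in the extrapulmonary part of the study. The documents do not support this. Section 4.2.1 names no disease, so a first-ever case may already attend a clinic here, while a lung case need not. No case mix is given either.

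**Conclusion.** The point holds as a possible source-population mismatch affecting the aPAF. The eligibility criteria create it, and no matching, named covariate or planned subgroup addresses it. Its direction and size cannot be determined from the documents. Under the assumed rates, formula and 40% share, the overall aPAF would be about 10.6% to 14.1% instead of 13.0%.

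Two stronger readings should be avoided. One takes the 7.0% to 15.8% range of step 4 as the error in the overall aPAF; that would require every in-patient to come from outside the followed-up population, which nothing in the documents suggests. The other says that section 6.2 subtracts one rate from all in-patients alike; the section says only that it adjusts for the background rate, for each virus and overall, by a cited method. Crude incidence among in-patients is unaffected. This is a worthwhile and inexpensive improvement, not a flaw that invalidates the study.

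**What to change.** 1. In section 5.2, add to the extraction list whether each in-patient was under follow-up at this hospital's out-patient clinics or physiotherapy department before admission. Fix the look-back window in advance. The field is not on the current list, so confirm that the clinical management system holds it.
2. In section 6.2, prespecify a sensitivity aPAF restricted to in-patients with such follow-up, reported beside the all-patient aPAF. The restriction should mirror the follow-up criterion of 4.2.1 only. The 14-day symptom exclusion in 4.2.2 cannot sensibly be applied to acutely admitted patients.
3. Describe the restricted figure as sharing the controls' source population, not as fully like-for-like, because age, disease mix and calendar time may still differ.

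**Cost.** One field, one analysis and less precision. Eligibility, recruitment and sample size do not change. If 60 of 100 in-patients qualify, the exact 95% interval for 20% detection widens from 12.7-29.2% (20/100) to 10.8-32.3% (12/60). Simulating binomial counts at the assumed 20% and 8%, with 100 controls throughout, the 95% range of the aPAF goes from about 3-23% to about 1-25%. Estimates for single viruses would be less precise still.

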4.1.2 Exclusion criteria

1. Admitted to any hospitals in the past 14 days
2. Respiratory virus testing performed in the past 14 days
3. Antiviral against respiratory virus given within the past 14 days
4. Not sufficient saliva

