4.2.2 Exclusion criteria

1. Admitted to any hospitals in the past 14 days
2. Respiratory virus testing performed in the past 14 days
3. Antiviral against respiratory virus given within the past 14 days
4. Onset of new respiratory or non-respiratory symptoms within the past 14 days
5. Not sufficient saliva

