5. STUDY PROCEDURES

5.1 Schedule of evaluations

5.1.1 Participants at the acute medical ward (in-patients)

On the day of enrollment:

- Inclusion and exclusion criteria
- Written informed consent
- Demographic information
- Questionnaire on vaccine history and symptoms
- Collection of saliva specimen

Follow-up after patient discharge

- Hospitalization data (length of stay, laboratory and radiological tests, treatment)

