5.2 Assessment and clinical data collection

Initial symptom assessment will be performed by trained research nurses at the medical or at outpatient clinics. At the time of enrollment, the following information will be collected from the patient by the research staff using a standard questionnaire:

- Symptoms and date of symptom onset
- Prior use of oseltamivir or zanamivir within 14 days
- Prior use of antibiotics within 14 days
- Attended out-patient clinic for the same illness
- Close contacts with respiratory symptoms in the past 7 days
- Receive influenza vaccine in the past season
- Receive pneumococcal vaccine

The following data will be extracted from the clinical management system:

- Age, sex, comorbidities
- National Early Warning Score (NEWS) at A&E (20) (respiration rate, oxygen saturation, need for supplemental oxygen, temperature, systolic blood pressure, heart rate, level of consciousness)
- Time of hospital admission and discharge
- Clinical findings
 - Underlying disease

- Clinical symptoms and signs during hospitalization
- Hematological, biochemical, microbiological, immunological, and radiological investigation results on admission
- Need for supplementary oxygen, positive pressure ventilation, intubation, admission to intensive care unit, coronary care unit or high dependency unit during the hospital stay
- Final diagnosis

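### Does the undated 14-day testing exclusion remove in-patients who were tested after arriving at A&E?

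*Combined protocol and SAP*

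**What the plan says.** In-patients must come to the acute medical ward through A&E and meet "Hospitalized for less than 24 hours at the time of recruitment" (section 4.1.1). Section 4.1.2 then lists three exclusions with a 14-day look-back: "Admitted to any hospitals in the past 14 days", "Respiratory virus testing performed in the past 14 days" and "Antiviral against respiratory virus given within the past 14 days". None states the day from which the 14 days are counted. The out-patient list in section 4.2.2 repeats all three and adds "Onset of new respiratory or non-respiratory symptoms within the past 14 days".

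Three other provisions bear on the point. Section 5.2 extracts from enrolled patients' records "Hematological, biochemical, microbiological, immunological, and radiological investigation results on admission", and its questionnaire asks about "Prior use of oseltamivir or zanamivir within 14 days". Section 5.1.1 places "Collection of saliva specimen" on the day of enrollment. Section 4.3 has the research nurse document why screened patients were ineligible or did not take part.

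**The concern.** A patient may spend time in A&E and then up to a day on the ward before the research nurse arrives. If a clinician has already ordered a respiratory virus test, exclusion 2, applied literally at recruitment, makes that patient ineligible. Clinicians tend to test when they suspect infection, so the excluded patients could be those most likely to be positive. In-patient incidence would then be too low, and so would the attributable fraction built on it.

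That would be awkward here. Section 2.1 criticises earlier work because testing followed symptoms, and the synopsis hypothesis is that incidence has been underestimated. The loss could not be repaired at analysis, because only enrolled patients give saliva. Repeating the exclusion for out-patients would not reliably balance it, since most of them have no acute illness for which to be tested.

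**Working it through.** **The text.** The plan states no figure on this point, so the wording comes first.

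1. Exclusions 1 and 2 share the same look-back phrase. At recruitment every in-patient is already in hospital, so exclusion 1, counted back from recruitment, would leave nobody to enroll. It works only if the index admission is outside the window.
2. The natural reading gives adjacent items with identical wording the same window. Exclusion 2 then concerns tests done before the present admission.
3. Section 5.2 collects admission microbiology from enrolled patients, and section 3.3.2 lists microbiological results as an outcome. This fits a plan in which work-up in the current episode does not disqualify. It is not conclusive, because microbiology need not include virus testing.
4. Section 2.1 sets out to avoid selection by clinical testing. Dropping patients because a clinician tested them would defeat that aim.

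**The size if the literal reading were used.** The documents give neither positivity nor the frequency of early testing, so every rate below is an assumption. Only n = 100 in-patients comes from the protocol (section 6.1).

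Let p be true in-patient positivity, f the share of otherwise eligible patients excluded, and p_t their positivity. Positivity among those left is p_u = (p - f × p_t)/(1 - f). With p = 0.25:

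| f | p_t | p_u | Shift (points) |
|---|---|---|---|
| 0.02 | 0.45 | (0.25 - 0.009)/0.98 = 0.2459 | -0.4 |
| 0.05 | 0.45 | (0.25 - 0.0225)/0.95 = 0.2395 | -1.1 |
| 0.10 | 0.35 | (0.25 - 0.035)/0.90 = 0.2389 | -1.1 |
| 0.10 | 0.45 | (0.25 - 0.045)/0.90 = 0.2278 | -2.2 |
| 0.10 | 0.25 | (0.25 - 0.025)/0.90 = 0.2500 | 0 |
| 0.10 | 0.10 | (0.25 - 0.010)/0.90 = 0.2667 | +1.7 |

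For scale, the 95% half-width at 25% and n = 100 is 1.96 × sqrt(0.25 × 0.75/100) = 8.5 points. In the -2.2 point case the standard error is sqrt(0.2278 × 0.7722/100) = 0.0419, so the bias is 0.0222/0.0419 = 0.53 standard errors. Coverage of a nominal 95% interval is Φ(1.96 - 0.53) - Φ(-1.96 - 0.53) = 0.917.

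A second set of assumptions gives larger effects. Let t_pos and t_neg be the shares of virus-positive and virus-negative patients tested before recruitment. Observed positivity is q = p(1 - t_pos)/[p(1 - t_pos) + (1 - p)(1 - t_neg)]. With p = 0.20:

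| t_pos | t_neg | Excluded | q | Shift (points) |
|---|---|---|---|---|
| 0.20 | 0.20 | 20% | 0.16/0.80 = 0.200 | 0 |
| 0.30 | 0.10 | 14% | 0.14/0.86 = 0.163 | -3.7 |
| 0.50 | 0.20 | 26% | 0.10/0.74 = 0.135 | -6.5 |
| 0.70 | 0.20 | 30% | 0.06/0.70 = 0.086 | -11.4 |

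The half-width at 20% is 1.96 × sqrt(0.20 × 0.80/100) = 7.8 points, which the last row exceeds. Across both tables the answer runs from a rise, through nothing, to a large fall. The assumed testing pattern sets the result; the plan does not.

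I give no figures for the attributable fraction. Section 6.2 takes its formula from a cited source, so any number would add one more assumption.

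**The case for a change.** The strongest reply is that exclusion 1 forces a non-literal reading because the literal one is absurd, whereas exclusion 2 can be applied literally without anyone noticing. A nurse could treat the two differently. Counting back from ward admission would also leave a test done in A&E, hours earlier, inside the window. One clause would settle both points, and patients wrongly excluded cannot be recovered.

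The textual part of this stands: the end date is unwritten, and no other section supplies it. What does not stand is the step from an unwritten date to lost patients. That needs staff to read two adjacent, identically worded items differently, early virus testing to be common, and tested patients to differ in positivity. The documents show none of the three. Nor would such a loss be hidden: the reasons for ineligibility recorded under section 4.3 would show how many patients exclusion 2 removed. As an illustration, 23 positives among 100 enrolled with 11 so excluded would bound positivity between 23/111 = 20.7% and 34/111 = 30.6%.

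It also goes too far to say that the exclusion can act only on the in-patient arm. An out-patient whose symptoms began 16 days ago and who was tested 12 days ago passes the new-symptom exclusion but is removed by the testing one. This is probably rare. If such out-patients were more often positive, removing them would lower the background rate and push the attributable fraction up.

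Exclusion 3 on antivirals has the same undated window, and section 5.2 asks about use over the same period. How treatment begun in the current episode is handled is a separate question and does not strengthen the case on testing.

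**Conclusion.** No change to the plan is needed. The reference date for exclusion 2 is missing, but the list works only with a window that closes before the index admission, and staff applying it would very likely use that window throughout. If so, and if the A&E attendance counts as part of the index admission, current-episode testing excludes nobody and the bias is zero.

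Under the literal reading the size and direction are unknown. The milder assumptions give -2.2 to +1.7 points, small beside a half-width of 8.5. The heaviest gives -11.4 points, but it requires 30% of otherwise eligible patients to be excluded, with positives tested far more often than negatives. The documents support none of these rates. The conclusion therefore rests on the pre-admission reading, not on the bias being small under every scenario. Writing the end date into the list would be harmless tidying; it would not alter the design, the sample size or the analysis.
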